**Blinding** 

The study design has a blinded assessment for the primary endpoint, which is a laboratory-based measurement to be performed by blinded operators who will receive coded samples. Although a double-blind design would be better, this would imply that the participants in two of the three treatment arms would have to swallow multiple placebo tablets, which could lead to unnecessary complications and possible dropouts.

Study arms

Phase II component

- Treatment Arm 1: Single dose of a tablet of ALB 400mg.
- Treatment Arm 2: Single dose of a tablet of FDC 400mg-18mg or 400mg-9mg (based on weight group).
- Treatment Arm 3: Daily dose of a tablet of FDC 400mg-18mg or 400mg-9mg for 3 days (based on weight group).

Version 4.0 21st January 2022

ALIVE Study

# Phase III component

- Treatment Arm 1: Single dose of a tablet of ALB 400 mg (active control arm).
- Treatment Arm 2: Single dose of a tablet of FDC 400mg-18mg or 400mg-9mg.
  - o For participants <45 kg of body weight at baseline: FDC of 400mg ALB-9mg IVM.
  - o For participants ≥45 kg of body weight at baseline: FDC of 400mg ALB-18mg IVM.
- Treatment Arm 3: Daily dose of a tablet of FDC 400mg-18mg or 400mg-9mg for 3 days.
  - o For participants <45 kg of body weight at baseline: FDC of 400mg ALB-9mg IVM.
  - o For participants ≥45 kg of body weight at baseline: FDC of 400mg ALB-18mg IVM.

Interim analysis is planned for this study. Refer to details in Section 9.4.6 (Planned Interim Analysis).

#### 4.2 SCIENTIFIC RATIONALE FOR STUDY DESIGN

# Rationale for randomization of treatment groups

Randomization will be used to minimize bias in the assignment of participants to any of the three groups, to increase the likelihood that known and unknown subject attributes (e.g. demographic and baseline characteristics) are evenly balanced between groups, and to enhance the validity of statistical comparisons across treatment groups.

# Rationale for not including participants with a single infection with A. lumbricoides

Due to the known good sensitivity of *A. lumbricoides* to ALB (current stand of care), participants who are only infected with this parasite will not be enrolled since no extra benefit is expected to be achieved with the FDC for this population. Moreover, in order to detect differences among treatment groups if participants with *A. lumbricoides* are included will mean a vast increase in the sample size which is unaffordable. Evaluation of participants with *A. lumbricoides* is an exploratory endpoint for those participants who are also infected with either hookworm, *T. trichiura* or *S. stercoralis*.

# Rationale for not including an IVM stand-alone arm

For the endpoints of the phase III trial, an ivermectin arm is not necessary firstly because it is not efficacious against *T. trichiura* (25) and hookworm in monotherapy. Although ivermectin is efficacious against *S. stercoralis*, the purpose of the FDC is to target a relevant public health burden of STH by

Version 4.0

ALIVE Study 21st January 2022

adopting a wide spectrum approach. Thus, the proposed FDC in the context of MDA, will tackle infections caused by *T. trichiura* (primary objective of the trial), hookworm and *S. stercoralis* (secondary objectives). Secondly, considering the low efficacy of ivermectin for *T. trichiura* and hookworm, it will not be ethically justifiable to perform a trial with an ivermectin alone arm when there will be no beneficence for the participants that fall into that arm. Furthermore, scientific evidence suggests and recommends

combination therapy with existing drugs against STH (42,43).

#### **Rationale for Site Selection**

All recruiting institutions are based in Africa and are partners and collaborators of the EDCTP-funded STOP project. Sites were invited based on experience with Good Clinical Practice (GCP), prevalence of the disease, extensive experience with IVM and ALB and ability to conduct the study in the required timeframe with the necessary number of participants.

#### **Rationale for Study Population Selection**

Participants between 5 and 18 years of age will be screened. This age range has been selected because of the high prevalence of STH in this population (it is the group most affected with STH), and the beneficial logistics implications of recruiting/enrolling at schools. The total number of participants to be screened depends on the prevalence rates of STH at the study site(s). A participant infected with a mixture of worms will be counted in the sample size for each worm that the participant is infected.

#### 4.3 RATIONALE FOR DOSE

# Albendazole (ALB) in Active control arm

Albendazole, through drug donations, is (along with mebendazole) the current standard of care for public health interventions for the control of STH as a public health problem. The recommended regimen is 400mg in single dose for individuals ≥2 years old. The safety of this drug in the regimen proposed for this clinical trial has been extensively evaluated and is a mainstay in MDA campaigns against LF and STH with negligible adverse events (1,44). The excellent safety profile allows to perform administration by non-health personnel during MDA activities (45). Choking in young children is the most frequent adverse event, therefore chewable formulations are routinely used.

Version 4.0 21st January 2022

ALIVE Study

**Fixed Dose Co-formulation (FDC)** 

The fixed dose co-formulation is composed of ALB and IVM. IVM has a wide therapeutic index, and has shown an excellent safety profile (36). Most of the severe adverse events of IVM have been described in patients with *Loa loa* microfilaremia, which has been associated to the death of numerous microfilariae and can produce life threatening events, especially encephalopathy (46). Otherwise, after administering a cumulative more than 1.32 billion treatments in mass drug administration programs mainly in Sub-Saharan Africa, it has been proven that IVM is a remarkably safe drug in humans. Most adverse side effects are minor, including mild gastrointestinal symptoms, dizziness, fatigue, and cutaneous allergic reactions. Biochemical abnormalities such as elevated liver enzymes and leukopenia are rarely seen (24,26,47,48).

Although IVM does not usually cross the blood-brain barrier, there are concerns about the possible neurotoxicity in case of an immature blood-brain barrier. Thus, IVM is generally not recommended for use in children under 3 or 5 years of age (depending on the country) or weighing less than 15 kg, in pregnancy and lactation, or in patients with diseases of the central nervous system. Still, a recently published individual patient data meta-analysis of children weighting less than 15 kg, including 1088 children, identified 18 adverse events (all mild and self-limiting) in 15 children (1.4%) (49). Recent data showed that IVM could be safe in younger children, even when administered at higher doses (29). There is a need to provide data about safety and pharmacokinetics (PK) of IVM in children younger than 5 years to allow for a broader use of the drug in patients who need it, given the high prevalence of several pathologies that could be managed with IVM in this age group.

FDC co-formulation of ALB and IVM is expected to have a safety profile similar to the co-administration of the drugs as delivered in MDA programs and clinical trials (50, 51). The high-fixed dose, as explained above in section 2.2, has been explored in a healthy volunteer study without added toxicity. Results from the comparative bioavailability study recently performed also support the safety profile of the FDC proposed in this phase II/III adaptive design. The safety results in the phase II component will guide the dose to be used in the phase III component. The phase II component will also provide data on the PK parameters of the FDC.

For this trial, the route of administration of the FDC is via oral dispersible tablets in either a one or three-dose regimen.

Version 4.0 21st January 2022

**ALIVE Study** 

#### 4.4 END OF STUDY DEFINITION

A participant is considered to have completed the study if he or she has completed all phases of the study including the last visit (study visit 6, Day 21 +/- 7 days) and scheduled procedures shown in the SOAs.

Although study participation ends at the follow-up visit 6 (21 days post-treatment), participants still harbouring STH at the follow-up visit will be referred for medical care at the local health reference centre for care. The drug of choice for treatment (ALB or IVM) will be provided free of charge.

Version 4.0 21st January 2022

**ALIVE Study** 

# STUDY POPULATION

#### 5.1 INCLUSION CRITERIA

In order to be eligible to participate in this study, an individual must meet all of the following criteria:

Specific Phase II/Phase III

- 1. Phase II: Positive infection test by microscopy for *T. trichiura*
- 2. Phase III: Positive infection test by microscopy for at least one of the following STH: *T. trichiura* hookworms, and/or larvae of *S. stercoralis*.

To be applied to Phase II and Phase III:

- 1. Weight ≥15 Kg (for phase II and III) and ≤ 45kg (only phase II).
- 2. Male or female, aged 5 to 18 years.
- Female participants who are ≥12 years old (or female who is post-menarche) must have a negative
  urine pregnancy test at screening or at the time of randomisation.
- 4. Ability to take oral medication, willingness to comply with all study procedures.
- 5. Parental acceptance to participate in the study by obtaining a signed and dated informed consent form approved by the Regulatory authorities. Written assent will also be obtained from children aged 12–17 years.

#### 5.2 EXCLUSION CRITERIA

An individual who meets any of the following criteria will be excluded from participation in this study:

- 1. Intake of ALB, mebendazole and/or IVM within the previous 3 months before screening.
- 2. Currently receiving warfarin.
- 3. Residence outside the study area or planning to move away in the four weeks following recruitment.
- 4. Epidemiological risk of *Loa loa* infection.
- 5. Serious medical illness, per investigator's criteria.
- 6. Any participant's condition preventing from the appropriate evaluation and follow-up, as per investigator's criteria.
- 7. Known hypersensitivity to any component of either study treatment.
- 8. Positive urine test, pregnant or first week post-partum.

Version 4.0 21st January 2022

ALIVE Study

#### 5.3 LIFESTYLE CONSIDERATIONS

During this study, participants will be asked to refrain from eating grapefruits or drinking grapefruit juice until study completion. Participants will be advised to have a light meal prior to study drug administration.

# 5.4 SCREEN FAILURES

Screen failures are defined as participants who consent to participate in the clinical trial but are not subsequently randomly assigned to the study intervention or entered in the study. For all screen failures, a minimal set of screen failure information is required to ensure transparent reporting of screen failure participants, to meet the Consolidated Standards of Reporting Trials (CONSORT) publishing requirements and to respond to queries from regulatory authorities. A screening log with minimal information will be collected for all participants that are screened. Minimal information includes demography, screen failure details, eligibility criteria, and any serious adverse event (SAE) recorded upon signing the informed consent form and followed up until resolution.

#### 5.5 STRATEGIES FOR RECRUITMENT AND RETENTION

Recruitment will be performed at schools and in the communities. No participant will be excluded from participation because of sex, race, or ethnicity or HIV status. The randomization process will ensure a balanced allocation of male and female participants in the trial.

Community mobilization and sensitization will be done by community health workers in the study area of each recruiting institution. The basic concepts about helminth infections, risk factors and prevention measures and available treatments will be shared with the community during this initial process. The main purpose of the clinical trial, and the activities foreseen will be explained to teachers, community leaders, and parents. Then, participants and/or legal representative or guardians/caretakers will be asked whether they are willing to participate to the study protocol.

The strategy to conduct the study in schools will help in the retention of participants for the study, however, recruitment will also be conducted at the community (house hold) level in order to reach the total number of participants needed for the trial. The short and focalized follow-up period will facilitate retention during the trial and minimize lost to follow-up of participants. For school recruitment, the school

Version 4.0

ALIVE Study 21st January 2022

calendar and timetables will be considered for scheduling the clinical trial visits in order to minimise interruption of scheduled activities.

House visits will be performed for study participants who miss school days on study-visits, in order to determine the cause of absenteeism and document any adverse events. A specific team will be identified and adequately trained to conduct these activities before the beginning of the trial.

The estimated total number of participants for the adaptive design is 1223 (*T. trichiura* 625, hookworm 312 and *S. stercoralis* 286). This sample size is powered to be able to measure efficacy for all three species in the phase III component, assuming a 10% lost to follow-up rate. The sample size for the phase II component is 20% of the total participants for *T. trichiura* (126 participants). The remaining 80% of the *T. trichiura* participants will be randomised in the phase III component. The total duration of the trial will be 18 months.

#### Justification for inclusion of children

The study population is children and young adults within the ages of 5 to 18. Current WHO Guidelines for Preventive Chemotherapy (PC) to control STH infections target at risk population groups, specifically young-children (12-23 months of age), pre-school age children (PSAC) (24-59 months of age) and schoolage children (SAC) (5 to 12 or 14 years of age) living in areas where the baseline prevalence of any STH ≥ 20%. The Guidelines also includes pregnant women after the first trimester, non-pregnant adolescent girls (10-19 years of age) and non-pregnant women of reproductive age (15-49 years of age) living under similar epidemiologic conditions as those explained above for children (52). The prioritization of the abovementioned groups is justified by the particular vulnerability of children to the morbidity caused by STH, with consequences in growth (10) and development. Recently updated information by WHO shows steady progress in the number of individuals achieved by these interventions, in a total of 101 countries requiring PC against STH for over 272 million PSAC and over 596 million SAC requiring PC worldwide, of whom approximately 69% were reached in 2017 according to WHO reports (53). Those children requiring PC for STH comprises of over 50% of the total target population, based on the WHO reports, and are therefore those that will mostly benefit from improvements in efficacy and in the logistic and economic advantages provided by regimens that allow larger coverage rates at diminished cost per treatment, as proposed by the innovative formulations and dosing strategies of this clinical trial. At the same time, the generation of evidence of safety and acceptability is also necessary in these age groups if an impact in the WHO Guidelines is sought.

Version 4.0 21st January 2022

**ALIVE Study** 

#### STUDY TREATMENT

# 6.1 STUDY TREATMENT ADMINISTRATION

#### 6.1.1 STUDY TREATMENT DESCRIPTION

FDC of ALB-IVM (400mg-18 mg and 400mg-9mg) will be developed and manufactured under Good Manufacturing Practices (GMP) by Laboratorios Liconsa, who will be responsible for the pharmaceutical development of the fixed-dose co-formulation and subsequent production, labelling, packaging and distribution to the trial sites.

For the control medication (study Arm 1), commercially available Albendazole tablets 400 mg manufactured under GMP will be provided by Laboratorios Liconsa for use in this study in accordance with approved labelling.

#### 6.1.2 DOSING AND ADMINISTRATION

# Phase II component

Participants will be randomly allocated with equal probability to receive either:

Treatment Arm 1: Single dose of a tablet of ALB

Treatment Arm 2: Single dose of a tablet of FDC

Treatment Arm 3: Daily dose of a tablet of FDC for 3 days.

and will be recruited by  $\mu g/Kg$  of IVM to be received in a sequential manner starting from Group 1 through to Group 3 as shown below:

- Group 1: receiving 300-391  $\mu$ g/Kg or ALB 400mg- 38 participants (body weight: 23-<30 Kg) will be recruited in this group. (FDC 400mg-9mg).
- Group 2: receiving 400-600  $\mu$ g/Kg or ALB 400mg– 38 participants (body weight: 30-45 Kg) will be recruited in this group. (FDC 400mg-18mg).
- Group 3: receiving 391-600 μg/Kg or ALB 400mg- 50 participants (body weight: 15-23 Kg) will be recruited in this group. (FDC 400mg-9mg).

Group 2 will receive FDC in an Albendazole 400mg/Ivermectin 18mg comp, groups 1 and 3 will receive FDC in an Albendazole 400mg/Ivermectin 9mg comp.

Version 4.0 ALIVE Study 21st January 2022

The table below shows the equivalent dose adjusted per weight received from 15 to 45 kg:

		Equivalent dose			Equivalent dose
Weight (Kg)	Ivermectin Dose	received (μg/Kg)	Weight (Kg)	Ivermectin Dose	received (μg/Kg)
15	9	600	31	18	581
16	9	563	32	18	563
17	9	529	33	18	545
18	9	500	34	18	529
19	9	474	35	18	514
20	9	450	36	18	500
21	9	429	37	18	486
22	9	409	38	18	474
23	9	391	39	18	462
24	9	375	40	18	450
25	9	360	41	18	439
26	9	346	42	18	429
27	9	333	43	18	419
28	9	321	44	18	409
2 9	9	310	45	18	400
30	18	600			

# Phase III Component

Participants will be randomly allocated with unequal probability, according to the specific expected cure rate by specie, to receive either:

**Treatment Arm 1**: Single dose of a tablet of ALB 400 mg (active control arm).

Treatment Arm 2: Single dose of a tablet of FDC 400mg-18mg or 400mg-9mg.

- o For participants <45 kg of body weight at baseline: FDC of 400mg ALB-9mg IVM.
- o For participants ≥45 kg of body weight at baseline: FDC of 400mg ALB-18mg IVM.

Treatment Arm 3: Daily dose of a tablet of FDC 400mg-18mg or 400mg-9mg for 3 days.

- o For participants <45 kg of body weight at baseline: FDC of 400mg ALB-9mg IVM.
- o For participants ≥45 kg of body weight at baseline: FDC of 400mg ALB-18mg IVM.

FDC will be provided as an oral dispersible formulation, while ALB will be a chewable pill. Both FDC and ALB will be taken with water after a light meal, followed by visual observation of the participant by the study physician at each site. Vomiting 1h post-treatment will require re-dosing. The participants will not

Version 4.0

**ALIVE Study** 

21st January 2022 be allowed more than one repeated dose. In case that a participant vomits following re-dosing during enrolment visit, the subject will be withdrawn from the trial and standard treatment will be offered according to national guidelines. Light meal is considered as a soft breakfast with a contribution of 15 g of fat. It might be defined as 250 cc of milk with tea or coffee, 1 tablespoon full sugar (25 g) and 25 g of fat biscuits. The expected nutrient contribution is approximately 312.8 calories: 38.43 g of carbohydrates,

4.81 g of proteins and 15.5 grams of fats.

Detailed instructions for dose administration, and storage conditions will be provided to each study site.

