**ALIVE Study** 

A conservative staged approach to weight-groups 1 through 3 will be taken. Enrolment will be sequentially done between weight groups 1 through 3, randomizing for all 3 treatment arms. Once weight group 1 is complete full source document verification of safety data up to Day 7 will be done and data will be shared with the DSMB and reviewed. If the stopping rule is not met, the DSMB will provide clearance to proceed with enrolment to the following weight group.

Once finalized recruitment of weight group 3, if safety data suggest that doses up to 600  $\mu$ g/kg of ivermectin for 3 days are possible, then the DSMB will provide clearance to proceed to the phase III component in order to evaluate safety and efficacy of the FDC when given for 1 or 3 days across the target age/weight range.

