# 6.5.1 RESCUE MEDICINE

All participants with a positive STH infection by microscopy on the last study visit 6 (Day 21 +/- 7 days) will be provided with rescue treatment. Participants with *S. stercoralis* infection will be offered ivermectin 3mg tablets at the currently standard regimen (200µg/kg) and participants with *A. lumbricoides*, hookworms and/or *T. trichiura* will be offered albendazole through their local health centres.

In case that a participant vomits following re-dosing during enrolment visit, albendazole 400mg single dose will be administered as standard treatment when recovered.

Version 4.0 21st January 2022

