**ALIVE Study** 

# STUDY INTERVENTION DISCONTINUATION AND PARTICIPANT DISCONTINUATION/WITHDRAWAL

#### 7.1 DISCONTINUATION OF STUDY INTERVENTION

On discontinuing study intervention, remaining follow up visits and study procedures should be completed as indicated in the SOAs. If a clinically significant finding is identified after enrolment, the investigator or qualified designee will determine if any change in participant management is needed. Any new clinically relevant finding will be reported as an adverse event (AE).

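### A child who vomits after re-dosing on Day 0 must be withdrawn from the trial, so one withdrawal assessment of unstated timing replaces the scheduled safety visits; this is not reconciled with section 7.1, and Days 1 and 2 have no specific rule

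*Protocol*

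**What the plan says.** The rules on vomiting are in Protocol section 6.1.2. "Vomiting 1h post-treatment will require re-dosing", and participants will not "be allowed more than one repeated dose". Neither statement is tied to a day or an arm. The consequence of a second vomit is tied to a day: "In case that a participant vomits following re-dosing during enrolment visit, the subject will be withdrawn from the trial". That sentence is printed under the Phase III heading of 6.1.2. Section 6.5.1 covers the same event without limiting it to a phase.

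Four other places bear on what happens next.

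- **Section 7.1:** "On discontinuing study intervention, remaining follow up visits and study procedures should be completed as indicated in the SOAs".
- **Section 7.2:** participants who discontinue the study are to be assessed for adverse events, with no timing given. It also lets the investigator discontinue a participant who cannot receive study drug as the protocol specifies. That is a discretionary reason and does not mention vomiting.
- **Section 8.1, Early Withdrawal, and the Withdrawal column of the schedules (1.4, 1.5):** final assessments are to be attempted. The column includes stool, physical examination, vital signs and adverse event monitoring, again with no date.
- **Treatment afterwards:** 6.1.2 refers to national guidelines; 6.5.1 says "albendazole 400mg single dose will be administered as standard treatment when recovered".

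Safety is the Phase II primary endpoint. Under section 4.1, once weight group 1 is complete, "full source document verification of safety data up to Day 7 will be done" and the DSMB reviews the data before enrolment moves to the next group.

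**The concern.** Withdrawal here is triggered by a possible sign of intolerance, so the children who leave the visit schedule are selected on something close to the Phase II primary endpoint. They have also been given two tablets on one day. Adverse events that begin after Day 0 are scheduled to be looked for on Days 1, 2, 3, 7 and 21, and a withdrawn child is outside that series. If the withdrawal assessment is done on Day 0, nothing scheduled remains to detect a later event, and the Day-7 data put before the DSMB would be thinner for exactly these children.

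There is also an asymmetry. On Day 0 the rule is mandatory and reaches all three arms. On Days 1 and 2 only the three-day arm takes drug, and no specific rule exists. The same clinical event can therefore end follow-up for one child and not for another, depending on the day and the investigator's discretion. This carries into efficacy, because the SAP scores a missing Day-21 result as failure.

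**Working it through.** **1. The plan's dose table.** Dose (µg/kg) = tablet strength (mg) × 1000 / weight (kg). In Phase II, "groups 1 and 3 will receive FDC in an Albendazole 400mg/Ivermectin 9mg comp" and "Group 2 will receive FDC in an Albendazole 400mg/Ivermectin 18mg comp". This gives 9 × 1000 / 15 = 600, 9 × 1000 / 23 = 391, 18 × 1000 / 30 = 600 and 18 × 1000 / 45 = 400. All 31 rows of the table in 6.1.2 reproduce to rounding.

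**2. Nominal Day 0 dose after one repeat.** Double the single-tablet dose:

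- 15 kg, 9 mg: 2 × 600 = 1200
- 22 kg, 9 mg: 2 × 9 × 1000 / 22 = 818
- 23 kg, 9 mg: 2 × 9 × 1000 / 23 = 783
- 30 kg, 18 mg (Phase II): 2 × 600 = 1200
- 45 kg, 18 mg: 2 × 400 = 800

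The largest planned daily dose is 600. The 30 kg figure belongs to Phase II under the protocol's tablet strengths. In Phase III a 30 kg child receives 9 mg, so two tablets give 2 × 300 = 600. SAP section 3.3 describes the Group 2 tablet differently (9 mg below 45 kg), which also needs reconciling.

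**3. Retained dose.** Let d be the single-tablet dose and a1, a2 the fractions retained from the first and second tablets. The documents give neither, so each is taken as anywhere between 0 and 1.

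- Vomits both tablets (withdrawn): d × (a1 + a2). With d = 600, from 0 to just under 1200.
- Vomits once and keeps the repeat (stays in): d × (a1 + 1). With d = 600, from 600 to just under 1200.
- Three-day arm with no vomiting (stays in): 3 × 600 = 1800 over three days.

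**4. What is lost and what remains.**

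- Lost: up to five scheduled visits (Days 1, 2, 3, 7 and 21), each with vital signs and adverse event monitoring, and the Day-21 stool.
- Kept: the observed Day 0 vomiting; one withdrawal assessment at no fixed time; follow-up of existing adverse events to resolution or a stable state (8.3.3.1); and a place in the safety denominator, which SAP 4.1 defines as everyone randomised.
- Efficacy: SAP 5.1.5 scores the missing Day-21 result as failure, with the baseline egg count carried forward. SAP 4.1 drops withdrawn children from the per-protocol set.

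**5. Scale.** In a weight group of 38, with FDC probability 0.4 + 0.4 = 0.8 (synopsis), about 0.8 × 38 = 30.4 children receive FDC. One such child is 1 / 30.4 = 3.3% of them.

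No double-vomiting rate is given. At an assumed 0.5% to 3%, the expected number is 0.5 to 3 of the 100 FDC children in Phase II and about 4 to 25 of the 427 + 419 = 846 in Phase III.

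For power, the plan's figure for *T. trichiura*, ALB against single-dose FDC, is 91% (116 and 223 participants; 23.7% and 43.7%; two-sided alpha 0.05 / 3). A pooled-variance two-proportion calculation gives 90.6%. Scoring the affected FDC children as failures multiplies 43.7% by 0.995 to 0.97, giving 43.5% to 42.4%, and power becomes 89.9% to 85.9%.

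**The case against.** Three stronger readings are tempting, and the documents do not support them.

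A reader might infer that the withdrawn children have the highest ivermectin exposure in the trial. They are defined by vomiting both tablets. At the same weight and first-dose retention, a child who keeps the repeat retains at least as much and stays in every visit. Three-day children may receive 1800 µg/kg over three days and also stay in. ALB children under the same rule receive no ivermectin. Only a nominal dose above the planned daily dose is shown.

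A reader might infer that these children vanish from the safety data. They do not. The vomiting happens under supervised dosing and a 3-hour observation period, the child remains in the safety set, adverse event assessment at discontinuation is required, and SAP 5.5.1 tabulates treatment-emergent events leading to study discontinuation. The Phase II stopping rules turn on serious adverse reactions and SUSARs, not on counts of vomiting. The loss is scheduled detection of later events.

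A reader might infer that 6.1.2 and 7.1 cannot both be followed. The protocol separates stopping study drug (7.1) from withdrawal from the study (7.2), and 6.1.2 can be read as a specific rule that places the child under 7.2. What stands is that a three-day child who vomits twice on Day 0 fits both descriptions, and nothing says which governs.

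Two smaller objections have weight. The vomiting text is printed under the Phase III heading, so its force in Phase II rests on 6.5.1 not being limited to a phase. And albendazole 400 mg may simply be what the national guidelines say, which cannot be checked from the documents.

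**Conclusion.** The concern holds as a gap in follow-up and an unreconciled set of rules. For a second vomit on Day 0, mandatory withdrawal replaces up to five scheduled visits with one undated assessment. For the same event on Day 1 or 2 there is only a discretionary reason in 7.2. Later events can be missed in children selected by possible intolerance who were given two tablets in a day, nominally up to 1200 µg/kg with true retention anywhere from 0 to just under that. An event missed in a child who stays in the denominator is counted as absent, so any error lowers the count of later events.

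The number affected is probably small. The rates used above are assumptions, and even at 3% the power for single-dose FDC against ALB stays above 80%. This is a matter of safety data, not of power. Its relevance to the Phase II DSMB reviews assumes that the rule applies in Phase II. It is worth correcting because the correction costs very little.

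**What to change.** Reconcile Protocol sections 6.1.2, 6.5.1, 7.1, 7.2 and 8.1 (Early Withdrawal), and state which phase or phases the vomiting text covers.

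For data collection only, state that a child with this event on Day 0, 1 or 2 stays in follow-up for the scheduled safety visits and the Day-21 stool unless consent is withdrawn. List re-dosed children separately in the safety data given to the DSMB, including the Day-7 reviews in Phase II.

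Sections 6.1.2 and 6.5.1 describe the treatment given afterwards differently, and the sponsor must reconcile them. No dosing, stopping or treatment rule is proposed here.

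The cost is protocol wording and one extra line in the DSMB report. The visits already exist in the schedule, and few children are likely to be affected.
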